3. OBJECTIVES

3.1 Primary Objective

- To assess outcomes associated with the application of the Consensus Document “Stent and Surgery-2” on perioperative antiplatelet therapy in patients with coronary stenting undergoing surgery.

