4. STUDY DESIGN

4.1 Summary of Study Design

The SAS registry will include any patient with previous coronary stenting undergoing any type of surgery or operative endoscopic/endovascular procedure at the participating Centers. Centers will be divided into two groups: Centers that routinely follow the recommendations of the SAS 2 Document and Centers that do not. The relevant clinical, procedural and outcome data (within index admission and at 30 days) will be entered in a specifically designed electronic case record form (eCRF).

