4.5.2 Screening

Screening for inclusion into the registry will be made at the time of preoperative evaluation: this will be made by the consultant cardiologist in cooperation with the anaesthesiologist and/or surgeon/endoscopist in charge of the operation.

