7. STATISTICS

7.1 The Number of Participants

Consecutive patients will be enrolled over one year of time at the participating Centers.

Cases and controls patients will be divided into those who will use Consensus Document “Stent and Surgery-2” (group 1) vs those who traditionally will be managed by local practice (group 2). On the basis of previous data reported SAS, a sample size of 1623 patients would be required to have a case-control matching 1:2, assuming a study power of 80% and 5% significance. Of those, 324 case-patients (20% of group 1) vs 162 control-patients (ratio 1:2) would be required for enrollment within one-year after implanted stents. Two preplanned interim analyses will be performed by an independent statistician when 800 and 1500 of patients will be enrolled.

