7.2 Description of Statistical Methods

Continuous numeric variables will report as means with SD and compared using the Student’s t- or Wilcoxon rank-sum test. Categorical variables will be presented as counts and percentages and will be compared using the chi-square or Fisher’s exact test. To examine the effect of significant factors on two different groups (Group 1 vs Group 2) the hazard ratio of the interaction term will be calculated. To identify the independent predictors for in hospital NACE, 30day MACE and 30-day BARC bleedings, first univariate and then multivariate logistic regression models will apply. The BARC bleedings will be considered according to type of surgery. Specifically, BARC bleedings grade ≥ 3 will be considered in patients undergoing cardiac surgery, and BARC bleedings grade ≥ 4 will be taken into account for non-cardiac surgery. Covariates for multivariable models will be selected on the basis of a backward stepwise algorithm in a Cox proportional hazards model. Additionally, to minimise group differences on confounding covariates between patients who will be managed with consensus document (group 1) and those who will be received local practice (group 2), a 1:2 propensity score matching would be used. Propensity scores will be calculated with logistic regression, with multiple imputation and backwards elimination with a significance level to stay of 0.05. To ensure that the comparison between two groups (group 1 vs group 2) would not be bias, the proportion of patients who will not received consensus document within center that traditionally used it, will be excluded. The results will be presented as ORs with 95% confidence intervals (CI) and p values. For all

analyses, a two-sided $P <0.05$ will be required for statistical significance. All data will be analyzed using the Statistical Package of Social Sciences version 20 (IBM SPSS, Chicago, IL).

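### Excluding patients who did not 'receive' the Consensus Document at SAS 2 centres limits dilution but may introduce selection; 'received' is undefined and no group comparison keeps these patients

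*Combined protocol and SAP*

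**What the plan says.** The exclusion is in Section 7.2: "the proportion of patients who will not received consensus document within center that traditionally used it, will be excluded". Its purpose is given in the same sentence: "To ensure that the comparison between two groups (group 1 vs group 2) would not be bias".

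The two groups are described in more than one way:

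- **By centre.** Section 4.1 separates "Centers that routinely follow the recommendations of the SAS 2 Document and Centers that do not".
- **By patient.** Section 7.1 contrasts patients for whom the document is used "vs those who traditionally will be managed by local practice (group 2"). Section 7.2 refers to "patients who will be managed with consensus document (group 1) and those who will be received local practice (group 2").

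The primary endpoint (Sections 4.2 and 6.1) is discontinuation of aspirin and/or a P2Y12 inhibitor without bridging. Section 7.2 plans 1:2 propensity matching, with the score model built by "backwards elimination with a significance level to stay of 0.05".

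The data items listed in Sections 4.5.3 and 4.5.4 include none for whether the document was consulted or followed. No sensitivity analysis of the exclusion is described. The predictor models for NACE, MACE and BARC bleeding are not stated to be restricted, but they are not described as group comparisons.

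**The concern.** An exclusion meant to prevent bias can create it if the reason for exclusion is related to the outcome. Here the link is plausible, because the document gives guidance on perioperative antiplatelet therapy and the primary endpoint is a perioperative antiplatelet decision. If a patient counts as not having *received* the document because management departed from it, group 1 is selected partly on behaviour close to its own endpoint. The overlap is partial: Section 2 shows that SAS 2 accepts wash-out in some cases and reserves bridging for selected patients.

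The wording *managed with* in Section 7.2 makes a judgement after entry the likelier reading. A judgement fixed at the preoperative evaluation is not ruled out, since "Screening for inclusion into the registry will be made at the time of preoperative evaluation". Even then selection is possible. If, for instance, the document were consulted less often before urgent surgery (an assumption), those patients would leave group 1 only. Matching would correct this only if urgency is recorded and survives elimination from the score model.

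At stake is whether a difference between the groups could be read as an effect of applying the document. If *received* is not recorded preoperatively, it may later be recoverable only from the management data that also define the endpoint.

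**Working it through.** **The plan's own figure.** Section 7.1 gives 1,623 patients, 80% power, 5% significance and 1:2 matching, but no event rates, so the total can be neither reproduced nor refuted. I split it as 1,623/3 = 541 in group 1 and 1,082 in group 2. That split is an assumption: the only split in Section 7.1 is 324 case-patients versus 162 controls, which runs the other way. The odds ratios (ORs) below do not depend on the split; the error rates and powers do.

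**Which definition the check uses.** It takes groups by centre (Section 4.1), so the exclusion removes patients who would otherwise be in group 1. On the patient definition (Sections 7.1 and 7.2) the same selection arises from the group definition itself.

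**1. Selection with no true effect.** All rates are assumed:

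- p = endpoint rate in both centre groups (0.30)
- q = share of SAS 2-centre patients excluded
- r = endpoint rate among the excluded
- m = share of the resulting shift that matching removes

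Formulas:

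- Retained rate before matching: x0 = (p − q·r)/(1 − q)
- After matching: x = p + (1 − m)(x0 − p)
- Apparent OR = [x/(1 − x)]/[p/(1 − p)]
- n1 = 541(1 − q) and n2 = 2·n1 (retained patients re-matched 1:2)
- Chance of a false benefit = Φ{[−1.96·SE0 − (x − p)]/SE1}, with SE0 pooled and SE1 unpooled; false harm uses the other tail

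Example, q = 0.20, r = 0.45, m = 0:

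- x0 = (0.30 − 0.09)/0.80 = 0.2625
- OR = (0.2625/0.7375)/(0.30/0.70) = 0.83
- n1 = 432.8, n2 = 865.6, SE0 = 0.02664, SE1 = 0.02627
- Φ[(−0.0522 + 0.0375)/0.02627] = Φ(−0.56) = 0.29

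| Excluded (q) | Their rate (r) | OR, m = 0 | False result, m = 0 | OR, m = 0.5 | False result, m = 0.5 |
|---|---|---|---|---|---|
| 20% | 30% | 1.00 | 2.5% each way | 1.00 | 2.5% each way |
| 5% | 45% | 0.96 | 5% benefit | 0.98 | 4% benefit |
| 10% | 45% | 0.92 | 10% benefit | 0.96 | 5% benefit |
| 20% | 45% | 0.83 | 29% benefit | 0.91 | 10% benefit |
| 20% | 15% | 1.19 | 28% harm | 1.09 | 10% harm |

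Clustering by centre and confounding between centres are ignored.

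**2. Dilution if everyone is kept.** Assume a true 23.5% versus 30%, and that patients without the document have the group 2 rate. The group 1 rate is then (1 − q)·0.235 + q·0.30.

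| Non-application (q) | Group 1 rate | Power, all kept | Power, excluded (if unbiased) |
|---|---|---|---|
| 0% | 0.235 | 79% | 79% |
| 5% | 0.238 | 75% | 77% |
| 10% | 0.2415 | 70% | 75% |
| 20% | 0.248 | 59% | 70% |

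If, in addition to 20% non-application, 10% of group 2 were managed with the document, the rates would be 0.248 versus 0.90·0.30 + 0.10·0.235 = 0.2935, and power 49%.

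**The case against.** The strongest reply is that Sections 7.1 and 7.2 define the groups by patient. On that reading, patients at SAS 2 centres who did not receive the document were never in group 1, and the rule keeps them out of the comparator. Likewise, a patient managed with the document at another centre is arguably outside group 2 already. This stands: the rule is one-sided only on the centre definition. It moves the selection into the group definition without removing it, and it leaves Section 4.1 in conflict with Sections 7.1 and 7.2.

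Second, an as-managed comparison is legitimate, and the primary objective, "To assess outcomes associated with the application of the Consensus Document", fits it. This also stands, and the choice of estimand belongs to the sponsor. The exclusion does reduce dilution, as the second table shows, so the stated rationale is incomplete rather than baseless.

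Third, every rate above is assumed, and the large error rates need 20% non-receipt at centres said to follow the document routinely. This stands too. It limits the severity of the point but does not answer it, because the plan gives no means of bounding the effect.

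A reader might infer that the rule favours SAS 2, or that it invalidates the comparison. The documents support neither. The direction depends on whether excluded patients have the higher or lower endpoint rate, and there is no bias if they resemble the rest. A reader might also infer that *received* goes unrecorded. The eCRF is drafted separately and is not in the file, and neither is the SAS 2 appendix, so the degree of overlap with the endpoint cannot be judged.

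**Conclusion.** The point holds as a should-fix. Section 7.2 presents as a safeguard an exclusion that trades dilution for possible selection, on a criterion it does not define, with no group comparison beside it that keeps these patients. On the centre definition the exclusion is the source of the selection; on the patient definition the grouping itself is.

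The size is unknown. Under the assumptions above (30% endpoint rate, no true effect, 541 versus 1,082), the distortion ranges from none to a 10–29% chance of a false result in one direction, against a nominal 2.5%. The upper range needs 20% excluded with an endpoint rate of 45% (false benefit) or 15% (false harm). At 5% excluded with a 45% rate it is 4–5%. Baseline matching can remove part of the shift, but not all of it if *received* reflects later management.

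**What to change.** 1. Reconcile Section 4.1 (groups by centre) with Sections 7.1 and 7.2 (groups by patient), and state which comparison is primary. That choice is the sponsor's.
2. In Section 7.2, add a prespecified propensity-matched comparison of group 1 with group 2 by centre group. Declare centre status before enrolment, keep every eligible patient, and report the result beside the as-managed comparison. This is the step that removes the selection described here. A mirror-image exclusion in group 2 would not, because document users would still be selected within group 1.
3. Define *received* without reference to discontinuation or outcomes, and record it at the preoperative evaluation in both groups.
4. Report the number, reasons and endpoint rate of the excluded patients.
5. Replace the statement that the exclusion ensures an unbiased comparison with one saying that it limits dilution but may introduce selection.

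**Cost.** One eCRF item, if not already there, one added analysis and revised wording. The drawback is the dilution shown above. Reported alongside, the centre-group comparison needs no new sample size. If it were made primary, restoring 79% power under the same assumptions would take about 1,806, 2,019 or 2,571 patients at 5%, 10% or 20% non-application. It would also remain exposed to differences between centres that matching does not capture.

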4.2 Primary endpoint

- Rate of discontinuation of P2Y12 inhibitors and/or aspirin (without bridging) in the first 3 months after PCI with low risk characteristics and 6 months after PCI with high risk characteristics or any antiplatelet therapy discontinuation without bridging therapy

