5. TREATMENT OF PARTICIPANTS

The Registry will record actual perioperative management strategies in patients with previous stent implantation undergoing surgical and operative endoscopic/endovascular procedures. A guidance for the perioperative management of antiplatelet therapy is provided by the Consensus Document SAS 2 issued by GISE. The document is enclosed as an Appendix to the present protocol. The recommendations can be accessed by the Investigators through a workable web application, which can be downloaded at <https://itunes.apple.com/us/app/stent-surgery/id551350096?mt=8>.

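### Exposure to the Consensus Document is largely a centre attribute, but 7.2 names no centre clustering, before or after matching, and 7.1 allows for none in its 5% and 80%

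*Combined protocol and SAP*

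**What the plan says.** Section 4.1 sets the comparison at centre level: "Centers will be divided into two groups: Centers that routinely follow the recommendations of the SAS 2 Document and Centers that do not". Section 7.2 then removes the off-protocol patients on one side: "the proportion of patients who will not received consensus document within center that traditionally used it, will be excluded". There is no matching rule for patients managed by the Document at the other centres.

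For analysis, 7.2 gives a general rule: "Categorical variables will be presented as counts and percentages and will be compared using the chi-square" or Fisher's exact test. It names logistic models for predictors and for the propensity score, and a Cox model for selecting covariates. To reduce confounding, "a 1:2 propensity score matching would be used". No specific test is assigned to the primary endpoint. No random effect, GEE, clustered variance, centre term or centre-level test is named, for the full set or the matched set.

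Section 7.1 gives 1,623 patients, "assuming a study power of 80% and 5% significance", and a subset of 324 plus 162 patients within one year of stenting. It gives no number of centres, ICC or design effect, and none was found elsewhere in the supplied text.

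**The concern.** The primary endpoint in 4.2 is stopping aspirin or a P2Y12 inhibitor without bridging. That is a decision by the treating team, and 7.1 itself describes the comparator as local practice. Patients at one centre are seen by the same cardiologists, anaesthesiologists and surgeons, so their outcomes plausibly resemble each other more than those of patients elsewhere.

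When exposure also follows the centre, the independent information about the group effect depends on how many centres there are as well as how many patients. A patient-level chi-square or logistic test ignores this. A chance difference in habits between two sets of centres can then be reported as an effect of the Document, with a p-value that is too small and an interval that is too narrow. Matching on patient covariates does not cure this: most group 1 patients must be matched to patients at other centres, and the matched patients still share their centre's habits.

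**Working it through.** **The plan's own figure.** The 1,623 can be neither reproduced nor refuted, because 7.1 gives no event rates, effect size or endpoint. Many rate pairs land near it: for example, 16% versus 11% at 1:2 needs 1,614. The clustering argument does not need the rates. It takes 80% power under independence as given.

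**Inputs.** From the documents: N = 1,623; one-year set 324 + 162 = 486; two-sided 5%; 80% power. Assumed: number of centres k, equal centre sizes, ICC of 0.01, 0.02 or 0.05, and exposure by whole centre.

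**Formulas.**
- Mean centre size m = N/k; design effect DE = 1 + (m − 1) × ICC.
- True error of the unadjusted test = 2 × [1 − Φ(1.96/√DE)].
- Power of a centre-adjusted test at the planned effect: noncentral t with k − 2 degrees of freedom and noncentrality (1.960 + 0.8416)/√DE = 2.8016/√DE.

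**Worked case.** For N = 1,623, k = 30 and ICC 0.05, m = 54.1 and DE = 1 + 53.1 × 0.05 = 3.66. Then 1.96/√3.66 = 1.025, so the error is 30.5%. The noncentrality is 1.465 against a critical value of 2.048 on 28 df, so power is 29.3%.

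| N, centres | ICC | DE | True error | Power |
|---|---|---|---|---|
| 1,623, 30 | 0.01 | 1.53 | 11.3% | 58.9% |
| 1,623, 30 | 0.02 | 2.06 | 17.2% | 47.0% |
| 1,623, 30 | 0.05 | 3.66 | 30.5% | 29.3% |
| 486, 30 | 0.01 | 1.15 | 6.8% | 71.2% |
| 486, 30 | 0.02 | 1.30 | 8.6% | 65.9% |
| 486, 30 | 0.05 | 1.76 | 14.0% | 53.2% |
| 486, 100 | 0.01 | 1.04 | 5.4% | 77.7% |
| 486, 100 | 0.02 | 1.08 | 5.9% | 76.2% |
| 486, 100 | 0.05 | 1.19 | 7.3% | 71.9% |

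At ICC 0 the error is 5% and the power 80%. A beta-binomial simulation of the first case (20,000 null runs, 10 versus 20 centres, 20% event rate) gave errors of 11.0%, 17.2% and 30.8%, in line with the formula.

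**Departures from the simple case** (30 centres, 1,623 patients, ICC 0.01 / 0.02 / 0.05). Each rests on one simulation set-up that was not independently repeated.
- 10% of patients at other centres counted in group 1: error 9.3 / 14.6 / 25.6%. With 25%: 8.2 / 11.2 / 19.7%.
- Unequal centre sizes (coefficient of variation about 0.75): 14.4 / 21.9 / 37.7%.
- 1:2 propensity-matched set (about 1,206 patients; 8 of the 30 centres in the smaller group): patient-level test 10.6 / 15.2 / 25.9%, against 4.7% at ICC 0.

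**Does the usual remedy hold 5%?** In the matched simulation, plain centre-clustered standard errors with a t reference on k − 2 df rejected 6.8 / 6.9 / 6.5% at 30 centres and 9.5 / 9.4 / 8.8% at 10. A t-test on centre proportions rejected 3.9 / 4.4 / 4.2% and 5.1 / 5.1 / 4.5%. By the formula, power at 10 centres, N = 1,623 and ICC 0.05 is only about 13%.

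**The case against.** The strongest reply is that every quantity driving the size is assumed. That is correct. With many small centres and a low ICC the effect is negligible, and nothing in the documents excludes that case. The power figures also presuppose that 80% holds under independence, which cannot be checked.

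Some stronger statements that a reader might infer are not supported:
- *That exposure is purely by centre.* The exclusion is one-sided, 7.1 words the groups by patient, and section 5 says "The recommendations can be accessed by the Investigators through a workable web application", with no limit to user centres. Mixing lowers the inflation, but in the simulation did not remove it.
- *That the plan nowhere states a number of centres.* The opening pages were not available. Only its absence from 7.1 and the supplied text can be stated.
- *That the models leave centre out.* Section 7.2 lists no covariates, so it can be said only that none of the methods names centre.
- *That clustering would make the comparison valid.* This is a non-randomised comparison of centres that already follow the Document with centres that do not. Differences in case mix or surgical practice are confounded with exposure, and a wider interval does not remove that bias.

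That the study is a registry does not answer the point: 7.2 still commits to two-sided P<0.05 and 95% intervals for the group comparison.

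**Conclusion.** The point holds, and the plan must be changed. Followed as written, 7.2 gives intervals that are too narrow for any positive within-centre correlation, and the 5% and 80% in 7.1 do not then hold. This is firm in direction and conditional on that correlation, which the nature of the primary endpoint makes plausible. The size is an illustration only: it runs from near-negligible (486 patients, 100 centres) to a several-fold excess over 5% (1,623 patients, 30 centres), depending on centre number, centre sizes, ICC and the degree of mixing. It is no evidence that 1,623 is itself a wrong calculation.

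**What to change.** In 7.2:
- Test the group effect with centre as the cluster, also in the matched set, by a small-sample-corrected method, for example bias-corrected clustered standard errors or GEE with a t reference on centres minus 2. These corrected versions were not simulated here, so their error should be checked for the actual centre layout.
- With roughly 30 or fewer centres, make a centre-level comparison of proportions primary and state its low power. Section 7.2 names Student's t for continuous variables only, so this use must be added explicitly.
- State how patients managed by the Document at other centres are classed.
- State that clustering corrects the error bars only and leaves systematic differences between Document and non-Document centres in place.

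In 7.1, give the number of centres, an assumed ICC with a range, and which set (all, matched or one-year) carries the comparison. Restate the power for that design rather than enrolling more patients, since 4.4.3 fixes enrolment at 12 months.

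The cost is SAP wording and a standard analysis, with no new clinical data. The analysis file must carry a centre identifier. The eCRF audit trail in 8.1 covers centres, but that alone does not show the identifier reaches the analysis file. The downside is wider intervals and a lower stated power.

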2. BACKGROUND AND RATIONALE

Every year more than 1 million PCIs are performed in United States and similar numbers in Europe^{1,2}. In more than 85% of cases a coronary stent is implanted³, with the ensuing need for prolonged antiplatelet therapy in order to prevent stent thrombosis (ST). The international Practice Guidelines recommend dual antiplatelet therapy (DAPT) with aspirin and a P2Y₁₂ receptor antagonist for at least one month after bare metal stent (BMS) implantation and for 6 months after drug eluting stent (DES)^{4,5}. In patients with acute coronary syndrome (ACS), DAPT should be prolonged up to 12 months.

Premature discontinuation of antiplatelet therapy is associated with a significant increase in the risk of ST⁶⁻⁹, an infrequent but lifethreatening event which occurs most of the times as acute myocardial infarction (MI), with a mortality rate of 10-40%. The single most important predictor of ST is the cessation of antiplatelet therapy¹⁰⁻¹². Previous studies demonstrated that premature discontinuation of antiplatelet therapy (permanent or transitory) after stent implantation occurs in 10-50% of patients^{7,13}, most frequently due to surgical interventions¹³.

It has been estimated that 4-8% of patients submitted to stent implantation undergo surgery within the first year³. The perioperative management of antiplatelet therapy represents a relevant issue, not only as it is epidemiologically relevant, but also because it may have significant clinical consequences¹⁷. A patient who experiences a perioperative MI has an inhospital mortality of 15-25%¹⁸⁻²⁰.

Perioperative management of antiplatelet therapies raises important challenges and safety concerns. On one hand, withholding therapy to reduce the risk of bleeding complications is associated with a heightened risk of ischemic events, including life-threatening stent thrombosis (ST), myocardial infarction (MI) and stroke [8-10]. Surgery leads to inflammatory, hypercoagulable and hypoxic states which are associated with plaque instability and perioperative

arterial thrombosis^{3,14}. Thus, the perioperative risk of ST and other cardiac ischemic events is high, particularly if antiplatelet therapy is discontinued^{15,16}. On the other hand, maintaining antithrombotic therapy may increase the risk of bleeding and the need for transfusions, which are both known determinants of poor prognosis [3-10].

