Defining the trade-off between ischemia and bleeding requires not only an understanding of the thrombotic risk of the individual patient, typically defined by the cardiologist, but also a clear understanding of the hemorrhagic risk specific to each surgical procedure, which requires the expertise of the surgeon. Although guidelines provide recommendations with respect to the perioperative management of antiplatelet and anticoagulant drugs, these have been developed primarily by cardiologists who may be less informed of the inherent bleeding risk of specific surgical procedures [11, 12]. Therefore, the surgical point of view is essential when it comes to issuing recommendations on how to manage antithrombotic therapies in the perioperative period. However, characterization of the perioperative bleeding risk of each surgical procedure is an area not addressed by current guidelines [11, 12].

On this background, the Italian Society of Interventional Cardiology (GISE) has previously promoted the creation of a task force integrating the expert opinions from a multidisciplinary collaboration between cardiologists, anesthesiologists, hematologists and surgeons, providing recommendations on the antithrombotic treatment regimen to be used in patients treated with coronary stents undergoing surgical and endoscopic procedures [13]. In particular, this led to the creation of a consensus document, called Surgery after Stenting (SAS), which provided practical recommendations for standardizing the approach to antithrombotic therapy management with respect to various types of surgery based on the predicted individual risk of thrombotic complications against the anticipated risk of surgical bleeding complications. A national registry surveyed the applicability of the recommendations in real-world clinical practice and supported

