6. DEFINITIONS OF THE ENDPOINT COMPONENTS

6.1 Antiplatelet therapy discontinuation

Antiplatelet discontinuation is defined as P2Y₁₂ inhibitors and/or aspirin withdrawal for >5 days at the time of surgical procedure without bridging therapy with antiplatelet agents in the first 3 months after PCI with low risk characteristics and 6 months after PCI with high risk characteristics or any any antiplatelet therapy discontinuation without bridging therapy at any time after PCI. A detailed description on the perioperative management of oral antiplatelet therapy will be obtained for both aspirin and P2Y₁₂ inhibitors (ticlopidine, clopidogrel, prasugrel, and ticagrelor). This includes the time delay from drug interruption to surgery as well as the time from surgery to reintroduction of therapy. The use of any bridging strategy will also be recorded. According to the SAS 2 Consensus Document, in selected patients at high risk for both bleeding and ischemic events, when withdrawal of oral antiplatelet therapy is required, bridging with cangrelor or with a short-acting intravenous glycoprotein IIb/IIIa inhibitor (GPI) (tirofiban or eptifibatide) can be considered.

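### Section 7.2 plans no absolute group difference with a confidence interval beside the odds ratio, so the balance of ischaemic and bleeding events is not shown in comparable units

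*Combined protocol and SAP*

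**What the plan says.** Section 7.2 sets the form of the results: "The results will be presented as ORs with 95% confidence intervals (CI) and p values". For descriptive comparison it adds: "Categorical variables will be presented as counts and percentages and will be compared using the chi-square or Fisher’s exact test". One other effect measure appears: "the hazard ratio of the interaction term will be calculated". That concerns whether certain factors act differently in the two groups; it is not the effect of group. The section also plans 1:2 propensity-score matching to reduce confounding between patients managed by the Consensus Document and patients managed by local practice. It names no risk difference, risk ratio or number needed to treat.

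The primary endpoint in Section 4.2 is a proportion: "Rate of discontinuation of P2Y12 inhibitors and/or aspirin", without bridging, within set periods after PCI. Section 6.1 widens it to "antiplatelet therapy discontinuation without bridging therapy at any time after PCI". Neither section gives an expected rate, and Section 7.1 gives none for the sample size. The only related figure is in Section 2, where premature discontinuation "after stent implantation occurs in 10-50% of patients".

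Section 2 describes the clinical problem as a balance: "Defining the trade-off between ischemia and bleeding requires not only an understanding of the thrombotic risk of the individual patient". Section 3.2 makes ischaemic and haemorrhagic events a secondary objective. For each type of surgery, Section 4.3 lists an ischaemic composite, a bleeding endpoint and a composite of the two, all at 30 days.

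**The concern.** A reader of the results will want to know how many ischaemic events are avoided or added per 1000 patients, how many bleeds are added or avoided, and how precisely each number is known. An OR answers none of these without a baseline risk. Two ORs that look like mirror images can correspond to absolute effects of quite different size when the two outcomes differ in frequency.

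The centres are not randomised. Section 7.2 plans matching because the crude groups are expected to differ, so the comparison that deserves most weight is the matched one. For that comparison the plan provides no absolute estimate with its uncertainty.

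A second, conditional issue concerns the primary endpoint. If unbridged discontinuation is common, readers who take the OR for a risk ratio will credit the Consensus Document with a larger effect than it had.

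**Working it through.** **The plan's own figure.** Section 7.1 gives 1623 patients for 80% power at 5% significance with 1:2 matching. It states no endpoint, rate or effect size, so the figure cannot be reproduced and does not show which effect measure the planners had in mind. Nothing below changes it.

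**Step 1: OR against risk ratio.** Let p be the control-group risk (assumed) and let the true risk ratio be 0.70 (assumed). Then OR = [0.7p/(1 − 0.7p)] / [p/(1 − p)].

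| Control risk | Risk in the other group | OR | Reduction if the OR is read as a risk ratio | True reduction |
|---|---|---|---|---|
| 2% | 1.4% | 0.696 | 30% | 30% |
| 5% | 3.5% | 0.689 | 31% | 30% |
| 10% | 7% | 0.677 | 32% | 30% |
| 20% | 14% | 0.651 | 35% | 30% |
| 30% | 21% | 0.620 | 38% | 30% |
| 40% | 28% | 0.583 | 42% | 30% |
| 50% | 35% | 0.538 | 46% | 30% |

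The gap is slight at 10% or below and becomes material from about 20–30%.

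The same can be seen at the effect that the study could just detect. Assume that 1623 splits 1:2 as 541 and 1082 (541 × 3 = 1623), with independent patients, 80% power and two-sided 5%. From a control risk of 50% the detectable risk is 42.7%, a risk ratio of 0.85 and an OR of 0.74. The OR suggests a 26% reduction where the risk falls by 15%.

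**Step 2: one OR, several absolute effects.** New odds = OR × p/(1 − p); new risk = odds/(1 + odds). Changes are events per 1000, at assumed control risks.

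| Control risk | OR 0.70 | OR 1.40 |
|---|---|---|
| 2% | −5.9 | +7.8 |
| 5% | −14.5 | +18.6 |
| 10% | −27.8 | +34.6 |
| 30% | −69.2 | +75.0 |

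**Step 3: a mirror-image pair.** Take an OR of 0.60 for ischaemia and 1/0.60 = 1.67 for bleeding. The baseline risks are assumptions, varied to show the range.

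- Ischaemia 4%, bleeding 8%. Ischaemia: odds 0.0417 × 0.60 = 0.0250, risk 2.4%, change −1.6 points. Bleeding: odds 0.0870 × 1.667 = 0.1449, risk 12.7%, change +4.7 points. The bleeding change is about three times the ischaemic one.
- Both 4%. Ischaemia −1.6 points as above. Bleeding: 0.0417 × 1.667 = 0.0694, risk 6.5%, change +2.5 points. The ratio is about 1.6.
- Ischaemia 8%, bleeding 4%. Ischaemia: 0.0870 × 0.60 = 0.0522, risk 5.0%, change −3.0 points. Bleeding +2.5 points. The ischaemic change is now the larger.

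The same two ORs therefore fit a bleeding excess three times the ischaemic gain, or an ischaemic gain larger than the bleeding excess. The ORs alone do not say which.

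**The case against.** The strongest reply is that the absolute information is already in the plan. Section 7.2 promises counts and percentages and does not confine them to the unmatched cohort. In a fixed-ratio matched sample, the difference between the two group percentages is the matched risk difference. This largely stands: a reader who infers that results appear only as ORs, or that the trade-off cannot be weighed at all, goes further than the documents allow. What remains missing is a commitment to tabulate the matched sample in this way, and a confidence interval for the difference.

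A second reply is that the composite of death, infarction, stent thrombosis and bleeding in Section 4.3 already puts both harms on one scale. It does, and it helps. But it counts its components equally and can hide effects in opposite directions, so it does not replace the two separate differences.

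A third reply concerns the primary endpoint. A reader might infer from the 10–50% in Section 2 that the endpoint is common and that its effect will look exaggerated. The documents do not support this. That range describes premature discontinuation after stenting in general, not unbridged discontinuation around surgery. At its lower end the OR (0.677) is close to the risk ratio (0.70). Nor is the OR biased; it misleads only when read as a risk ratio.

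Finally, Section 7.1 uses the term case-control, which might suggest that risks cannot be estimated. Its groups are defined by management, not by outcome, and patients are enrolled consecutively, so risks and their difference can be estimated.

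**Conclusion.** The point holds in a limited form. The OR is the only group-effect measure planned with a confidence interval, and no absolute difference with an interval is planned for the matched comparison, although the balance of ischaemia and bleeding is part of the registry's question.

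The size of the problem depends on rates that the documents do not give. In the assumed examples, a mirror-image pair of ORs corresponds to a bleeding change between about 0.8 (2.5/3.0) and 3 times the ischaemic change. For the primary endpoint, reading the OR as a risk ratio would turn a true 30% reduction into an apparent 32% at a control risk of 10%, or 46% at 50%.

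The documents do not support the view that the OR is wrong or must be demoted; which measure leads is a matter of preference. This is a reporting improvement of minor severity. It affects neither the stated sample size nor the data collected.

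**What to change.** In Section 7.2, add that for the primary endpoint and for the 30-day ischaemic and bleeding endpoints each OR will be accompanied by the risk difference with 95% CI, estimated in the propensity-matched sample. Show the ischaemic and bleeding differences side by side, separately for cardiac and non-cardiac surgery.

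State how the variance will be obtained. It should respect the matched sets and the clustering of patients within centres. Section 4.1 forms the groups by centre, so matched sets will cross centres and both features matter. Say also how estimates will be pooled over the multiple imputations named in Section 7.2.

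First reconcile the bleeding definition. Section 4.3 uses BARC grade 3 or higher for non-cardiac and grade 4 or higher for cardiac surgery, while Section 7.2 states the reverse. Until that is settled, neither an OR nor a risk difference for bleeding is well defined.

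The cost is a short addition to the text, one more column per table and a little more analysis work; no new data are needed. The downside for the authors is that the effect may look less striking than the OR.
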